NON-INTERVENTIONAL STUDY (NIS) PROTOCOL

Study information

Title	Patterns of Real-World Isavuconazole use, Effectiveness, Safety, and Healthcare Resource Utilization—a Retrospective Chart Review Study of Patients With Mucormycosis or Invasive Aspergillosis (PRISMA)
Protocol number	C3791008
Protocol version identifier	Final version 1.1
Date	27 July 2020
Active substance	Isavuconazole (ATC code J02AC05)
Medicinal product	Cresemba®
Research questions and objectives	
Primary objectives:
 
• To document real-world clinical outcomes (all-cause mortality, overall response) of isavuconazole in patients with invasive aspergillosis or mucormycosis who are receiving treatment in routine clinical practice in Europe (France, Germany, Italy, Spain, and the United Kingdom).• To assess real-world safety (isavuconazole-related adverse events or serious adverse events) of isavuconazole in patients with invasive aspergillosis or mucormycosis receiving treatment in routine clinical practice in Europe. 
Secondary objectives:

	
 • To describe demographic and clinical characteristics of patients with invasive aspergillosis or mucormycosis receiving isavuconazole in routine clinical practice in Europe. • To document treatment patterns among patients with invasive aspergillosis or mucormycosis receiving isavuconazole in routine clinical practice in Europe. • To quantify HCRU among patients with invasive aspergillosis or mucormycosis receiving isavuconazole in routine clinical practice in Europe.
Authors	
PPD [REDACTED] PhD PPD [REDACTED] Pfizer Inc. [name]
 
PPD [REDACTED] MD, MScPH PPD [REDACTED] Evidera [name]

Co-authors	
PPD [REDACTED] MPH PPD [REDACTED] Pfizer Inc. [name]
 
PPD [REDACTED] MD, MBA PPD [REDACTED] Pfizer Inc. [name]
 
PPD [REDACTED] PhD PPD [REDACTED] Evidera [name]

	PPD	MD
	PPD	
	PPD	
	[name]	
	[name]	
	PPD	PhD
	PPD	
	Evidera	
	[name]	
	[name]	

2. LIST OF ABBREVIATIONS

Abbreviation	Definition
AE	adverse event
AEM	Adverse Event Monitoring
AIDS	acquired immunodeficiency syndrome
ALT	alanine aminotransferase
AST	aspartate aminotransferase
ATC	anatomical therapeutic chemical
BAL	bronchoalveolar lavage
BDG	beta-(1,3)-D-glucan
CI	confidence interval
CIOMS	Council for International Organization of Medical Sciences
CMV	cytomegalovirus
COPD	chronic obstructive pulmonary disease
COVID-19	coronavirus disease of 2019
CRF	Case report form; also referred to as electronic data record
CRO	contract research organization
CSA	clinical study agreement
CT	computed tomography
DHHS	Department of Health and Human Services
EDC	electronic data capture
EMA	European Medicines Agency
ENCePP	European Network of Centres for Pharmacoepidemiology and Pharmacovigilance
EORTC/MSG	European Organization for Research and Treatment of Cancer/Mycosis Study Group
ER	emergency room
EU	European Union
FDA	Food and Drug Administration
FWA	Federal-Wide Assurance
FU	follow up
GEP	Good Epidemiological Practice
GM	galactomannan
GPP	Good Pharmacoepidemiology Practices
HCP	healthcare provider
HCRU	health care resource utilization
HEOR	health economics and outcomes research
ICD-9	International Classification of Diseases, 9th Revision
ICD-10	International Classification of Diseases, 10th Revision
ICF	informed consent form
ICMJE	International Committee of Medical Journal Editors
ICU	intensive care unit
ID	Identifying number

Abbreviation	Definition
IEA	International Epidemiological Association
IEC	Independent Ethics Committee
IRB	Institutional Review Board
ISPE	International Society for Pharmacoepidemiology
ISPOR	International Society for Pharmacoeconomics and Outcomes Research
KM	Kaplan-Meier
LOS	Length of stay
MRI	magnetic resonance imaging
NIS	non-interventional study
NISMF	NIS master file
OHRP	Office for Human Research Protections
PRISMA	Patterns of Real-World Isavuconazole use, Effectiveness, Safety, and Healthcare Resource Utilization—a Retrospective Chart Review Study of Patients With Mucormycosis or Invasive Aspergillosis
QT	QT interval
RTI	Research Triangle Institute
RTI-HS	RTI Health Solutions
RWE	real world evidence
SAE	serious adverse event
SAP	Statistical Analysis Plan
SECURE	A Phase III, Double-Blind, Randomized Study to Evaluate Safety and Efficacy of BAL8557 Versus Voriconazole for Primary Treatment of Invasive Fungal Disease Caused by Aspergillus Species or Other Filamentous Fungi
SOP	standard operating procedure
TDM	therapeutic drug monitoring
UK	United Kingdom
US	United States
VITAL	Open-Label Study of Isavuconazole in the Treatment of Patients with Aspergillosis and Renal Impairment or of Patients with Invasive Fungal Disease Caused by Rare Moulds, Yeasts or Dimorphic Fungi

4. ABSTRACT

Study title: Patterns of Real-World Isavuconazole Use, Effectiveness, Safety, and Healthcare Resource Utilization—a Retrospective Chart Review Study of Patients With Mucormycosis or Invasive Aspergillosis (PRISMA)

Rationale and background: Invasive aspergillosis and mucormycosis are rare, life-threatening fungal infections associated with high mortality.^{1,2} Treatment of invasive aspergillosis usually includes antifungal medications such as voriconazole or isavuconazole.¹ Initial treatment of mucormycosis typically includes surgery to remove infected tissues and antifungal treatment with amphotericin B.¹

Cresemba® (isavuconazole) is an antifungal agent whose mechanism of action involves blocking the production of a key component of the cell membrane of fungi, thus weakening the membrane and preventing fungal cell growth.³ Isavuconazole demonstrated non-inferiority compared to voriconazole with improved safety profile in the SECURE clinical trial for patients with invasive aspergillosis (phase 3, randomized, double-blind, comparative-group; NCT00412893).⁴ Additionally, in the VITAL clinical trial (single-arm, open-label; NCT00634049), isavuconazole was well tolerated and showed activity against mucormycosis with efficacy comparable to that of amphotericin B in a matched case-control analysis.⁵ Isavuconazole was subsequently approved by the United States (US) Food and Drug Administration (FDA) and the European Medicines Agency (EMA) in 2015.

Following market authorization in 2015, real-world evidence (RWE) from European Union (EU) is needed for further insight into isavuconazole use outside of a trial setting. The current study is a retrospective, multi-country chart review to be conducted in five European countries (France, Germany, Italy, Spain, and the United Kingdom [UK]), designed to obtain RWE to increase the knowledge of isavuconazole patterns of use, clinical response, HCRU, and safety in clinical practice.

Research objectives: The primary objectives are to document real-world clinical outcomes (all-cause mortality, overall response) and assess real-world safety (isavuconazole-related adverse events [AEs] and serious adverse events [SAEs]) of isavuconazole for patients with invasive aspergillosis or mucormycosis receiving treatment in routine clinical practice in Europe (France, Germany, Italy, Spain and the United Kingdom). The secondary objectives include describing demographic and clinical characteristics, documenting treatment patterns, and quantifying health care resource utilization (HCRU) among patients with invasive aspergillosis or mucormycosis receiving isavuconazole in routine clinical practice in Europe.

Study design: A retrospective observational cohort study will be conducted, involving the review and abstraction of data from the medical records of patients diagnosed with invasive aspergillosis or mucormycosis who received treatment with isavuconazole. The target sample is approximately 600 patients across 22 sites located in Europe.^a De-identified data on patient demographics, disease characteristics, treatment effectiveness, safety outcomes,

^a Dependent on interest in participation and the number of eligible patients each site can contribute, the total number of sites enrolled as well as patients per site could increase/decrease.

isavuconazole treatment patterns, and HCRU will be collected from patient medical records and entered into an electronic data capture (EDC) system by site staff. As this study is retrospective, information pertaining to patient care will already be documented in patient medical records at the time of chart abstraction.

Population: Adult patients (aged ≥ 18 years) who received isavuconazole for the treatment of invasive aspergillosis or mucormycosis in the hospital setting.

Study sites: Although the target number of sites is 22 sites, the total number of sites enrolled will depend on site interest, availability of its staff (considering the COVID-19 pandemic), and access to eligible medical records. Invasive aspergillosis and mucormycosis are rare fungal infections; thus, it is expected that the pool of potential patients across sites will be small. The sites will be hospital based; thus, the patient population will consist of those who were either hospitalized or attending a hospital at the initiation of isavuconazole therapy.

Patient population: Inclusion criteria: Patients must be aged ≥ 18 years at isavuconazole initiation, have a record of a diagnosis of invasive aspergillosis or mucormycosis at the time isavuconazole was initiated (regardless of whether this diagnosis is suspected or confirmed),^b and have received at least one dose of isavuconazole during the eligibility period (October 15, 2015, to June 30, 2019).

Exclusion criteria: Patients who did not receive at least one dose of isavuconazole for treatment of invasive aspergillosis or mucormycosis within the eligibility period.

Data source/data collection: Retrospective data will be abstracted from the medical records of patients and entered into an EDC system by trained local site staff. It is estimated that data abstraction will be completed in approximately 7 months from the point at which the first patient is included in the study (estimated to be from August 2020 to March 2021 for all countries except Italy, and from October 2021 to January 2022 for Italy).^c

^b Documented cases of invasive aspergillosis or mucormycosis will be included (providing the patient meets all other study inclusion criteria), regardless of whether the diagnosis is classified as being ‘suspected’ or confirmed via mycological or radiological assessments (this includes European Organization for Research and Treatment of Cancer/Mycosis Study Group [EORTC/MSG] classification of “proven,” “probable,” and “possible” invasive fungal disease). All available sources will be used to confirm diagnosis (including any text in the medical records [eg, discharge diagnosis] and *International Classification of Diseases, 10th Revision* [ICD-10] codes, if available). The level of documentation in the medical records is expected to vary by healthcare provider (HCP) and by site/country.

^c Dates of medical record abstraction are subject to change based on the volume of potentially eligible patients during the timeframe of the current eligibility period, the timing of study start-up, and the impact of the COVID-19 pandemic on site staff availability.

Patients who initiate isavuconazole treatment (index event) during the eligibility period (October 15, 2015, to June 30, 2019)^d will be identified and screened for inclusion/exclusion criteria for enrollment into the study. The two main study periods for data collection from each patient's medical chart are as follows:

- **Pre-index event period:** Baseline data on demographics and medical history will be collected based on all available information in medical records before the index event.
- **Post-index event period:** The timeframe for follow-up data collection will begin one day post-index treatment initiation and end at the earliest of the following: six-months post-index treatment discontinuation, death, loss to follow-up, or December 31, 2019. Key timepoints of interest for assessment of clinical outcomes (mortality and overall response), and safety will be assessed at 6 weeks, 12 weeks, and 24 weeks after initiation of index treatment.

Variables: Categories to be abstracted from the medical records if available include, but are not limited to, the following:

- Demographic, medical history, and clinical characteristics (eg, age, sex, history of invasive fungal infection and prior antifungal treatments, fungal disease characteristics such as diagnosis, mycological confirmation, date of diagnosis, and other comorbidities including underlying illness/risk factors for invasive aspergillosis and mucormycosis).
- Clinical outcomes (eg, overall response [including clinical response, mycological response, radiological response], and mortality).
- Safety outcomes (AEs and SAEs).
- Isavuconazole treatment patterns (eg, formulation, dosage [loading and maintenance], duration, treatment changes (including dosage adjustments, switching, and discontinuation), and concomitant medication).
- Health care resource utilization (eg, length of stay [LOS], emergency room [ER] visits, intensive care unit [ICU] visits and LOS, inpatient hospitalizations, and planned and unplanned outpatient visits).

Study size: Precision estimates were generated based on the all-cause mortality rate at day 42 for patients with invasive aspergillosis who received isavuconazole in the SECURE trial.⁴ A sample size of 150 to 200 patients is expected to yield a reasonable margin of error (between 5.00% and 6.25%) for estimating a 95% confidence interval (CI) for the mortality

^d The eligibility period end date is subject to change based on timing of medical record abstraction and anticipated number of potentially eligible patients during the proposed eligibility timeframe.

rate. However, 95% CIs may be wider for analyses of rare events or analyses conducted in small subgroups.

As mucormycosis is rare, sample size for this population is expected to be low and limited by the availability of patient medical records at sites. All eligible patients with mucormycosis will be included. Based on the observed weighted all-cause mortality rate in the sample of mucormycosis patients (n = 37) in the VITAL trial of 33%, such a sample would allow to estimate the mortality rate within a precision of 15%.

Data analysis: Data analysis will be primarily descriptive. Mean, standard deviation, median, minimum, and maximum, interquartile range, and range will be provided for continuous variables; numbers and percentages for each category will be provided for categorical variables. Time to event outcomes will be assessed using the Kaplan-Meier (KM) method and will be reported as descriptive statistics (eg, median time to event) with 95% CIs. The statistical analysis plan (SAP) will provide a detailed description of analytic populations, analyses to be performed, and methods to deal with missing data and censoring.

Milestones:

Completion of feasibility assessment: October 15, 2019

Start of data collection: August 10, 2020

End of data collection: January 22, 2022

Interim study report (ex-Italy): July 22, 2021

Final study report: May 26, 2022

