9.2.2. Inclusion Criteria

Patients must meet all of the following inclusion criteria to be eligible for inclusion in the study:

1. Patient must be aged ≥ 18 years at the time of isavuconazole initiation.
2. Patient must have a record of a diagnosis of invasive aspergillosis or mucormycosis in their medical record at the time isavuconazole was initiated (regardless of whether this diagnosis is suspected or confirmed).ⁱ
3. Patient must have received at least one dose of isavuconazole during the eligibility period (October 15, 2015, to June 30, 2019).^j

ⁱ Documented cases of invasive aspergillosis or mucormycosis will be included (providing the patient meets all other study inclusion criteria), regardless of whether the diagnosis is classified as being 'suspected' or confirmed via mycological or radiological assessments (this includes EORTC/MSG classification of "proven," "probable," and "possible" invasive fungal disease). All available sources will be used to confirm diagnosis (including any text in the medical records [eg, discharge diagnosis] and ICD-10 codes, if available). The level of documentation in the medical records is expected to vary by HCP and by site and/or country.

^j The eligibility period end date is subject to change based on timing of medical record abstraction and anticipated number of potentially eligible patients during the proposed eligibility timeframe.

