9.2.3. Exclusion Criteria

Patients meeting any of the following criteria will not be included in the study:

1. Patients who did not receive at least one dose of isavuconazole for treatment of invasive aspergillosis or mucormycosis within the eligibility period.

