9.10. Quality Control

The development of the protocol and SAP will follow Pfizer's internal standard operating procedures (SOPs), which include detailed review rounds. Quality control of the statistical programming will follow the CRO's SOPs.

The CRO will follow SOPs and quality-control processes that address patient data security to ensure that patient data (as well as other confidential data) remain secure and intact. The EDC system has built-in edit checks and validations and supports electronically generated and manual queries.

Patient confidentiality will be strictly maintained. Access to the EDC system will be regulated via a hierarchical username and password control. Subject data will be de-identified through design of data entry fields that do not permit the entry of identifying information such as initials, date of birth, date of diagnoses/treatments/admissions, or center-assigned patient identifiers. Only trained site staff will enter data into the electronic CRFs. Patients' ages in whole years, but not date of birth, will be entered. Dates related to diagnosis, treatments, hospital admissions, discharges, etc. will be entered by the physician; the EDC system will calculate durations. Dates will not be stored by the EDC system and will not exist within the data set. No patient identifiers used by sites will be entered; rather the EDC program will automatically assign a study identifying number (ID) to each patient. The de-identified data as entered into the EDC system will be visible to the CRO and the Sponsor, but only center staff will be able to trace a study ID number to a patient identity, a necessary measure to allow center staff to respond to data queries raised by the CRO later.

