**Figure 1 Overview of Study Periods and Examples of Eligible Cases**

### 4.2 STUDY PERIODS

[figure not shown]
The index event is defined as the first initiation of isavuconazole treatment for the invasive fungal infection. The index event serves as the point at which (1) a patient

PFIZER CONFIDENTIAL

qualifies for study inclusion, (2) patient follow-up begins, and (3) the patient becomes at risk for experiencing study outcomes. Study periods for data extraction and variable assessment are defined relative to the index event (Figure 1).

- **Eligibility period:** The index date must occur within the eligibility period, which is the timeframe wherein potentially eligible patients are identified for enrolment. *The dates comprising the eligibility period will be October 15, 2015 (date of isavuconazole approval by the EMA in the EU), to June 30, 2019. The end date of the eligibility period ensures that the latest date of isavuconazole initiation will occur at least 6 months before the end of December 2019 (after which point the medical records may contain data related to the COVID-19 pandemic, which is not of interest for this study). This definition will allow for a minimum of 6 months of follow-up from the date of isavuconazole initiation unless the patient dies or is lost to follow-up within this timeframe.*
- **Pre-index period:** *Baseline data on demographics and medical history will be collected based on all available information in medical records before the index event.*
- **Post-index period:** *The timeframe for follow-up data collection will begin one day post-index treatment initiation and end at the earliest of the following: 6 months after post-index treatment discontinuation, death, or loss to follow-up (Figure 1 and Figure 2). Key timepoints of interest for assessment of clinical response and safety will be at 6 weeks, 12 weeks, and 24 weeks after initiation of index treatment (Figure 2).*

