### 6.3 ANALYSIS OF CLINICAL OUTCOMES

Each clinical outcome will be analyzed using counts and frequencies at weeks 6, 12, and 24, along with other descriptive information about the clinical outcome itself.

Additionally, time-to-event analyses anchored on the index date of isavuconazole initiation will be performed using the KM method. For each clinical outcome, the time-to-event analyses will result in a KM plot with summary statistics, including survival-time quartiles and KM estimates at weeks 6, 12, and 24 with accompanying 95% CIs. All analyses will be performed for invasive aspergillosis patients, mucormycosis patients, and for the total study population. If subgroup analyses are pursued, Cox regression will be employed to derive HRs and accompanying 95% CIs.

For the death outcome, patients will be categorized as dead, alive, or unknown at each timepoint of interest, and primary cause of death will be tabulated (Appendix 1, Analysis Table 5.1). For KM analyses, a documented death will comprise the event, and patients will be censored at the date when they are last known to be alive (Appendix 1, Analysis Figure 1; Appendix 1, Analysis Table 5.2).

For the clinical response outcome, patients will be categorized as having clinical success, having clinical failure, or unknown response at each timepoint of interest will be tabulated (Appendix 1, Analysis Table 6.1). In addition, rates of reactivation of the same infection and rates of new infection will be documented overall and specific to whether these events occurred during isavuconazole treatment. For KM analyses, clinical response will comprise the event, and patients will be censored at the earliest timepoint of any of the following: loss to follow-up, end of study, or death (Appendix 1, Analysis Figure 2; Appendix 1, Analysis Table 6.2).

For radiological response, patients will be categorized as having a success, not having a response, unknown response, or not applicable (for the first assessment) at the relevant timepoints of interest (Appendix 1, Analysis Table 7.1). Additionally, radiological examination type and bodily location of the examination will be tabulated. For KM analyses, radiological response will comprise the event, and patients will be censored at the earliest timepoint of any of the following: loss to follow-up, end of study, or death (Appendix 1, Analysis Figure 3; Appendix 1, Analysis Table 7.2).

PFIZER CONFIDENTIAL

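### No criterion requires isavuconazole to have been started at the participating hospital; if patients transferred in on treatment are included, survival counted from initiation without delayed entry may understate primary mortality

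*Protocol*

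**What the plan says.** Protocol section 4 (Study sites) and section 9.2.1 describe the cohort by where patients were when treatment began: "the patient population will consist of those who were either hospitalized or attending a hospital at the initiation of isavuconazole therapy". The hospital is not identified as the participating one.

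The criteria in Protocol 9.2.2, repeated in SAP section 3, cover age, diagnosis and exposure. On diagnosis: "Patient must have a record of a diagnosis of invasive aspergillosis or mucormycosis in their medical record at the time isavuconazole was initiated". On exposure: "Patient must have received at least one dose of isavuconazole during the eligibility period". The only exclusion, in Protocol 9.2.3, removes "Patients who did not receive at least one dose of isavuconazole for treatment of invasive aspergillosis or mucormycosis within the eligibility period". None of these names the place of the first dose.

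SAP 4.2 defines the index event as first initiation for the infection and says that at this point the patient "qualifies for study inclusion, (2) patient follow-up begins, and (3) the patient becomes at risk for experiencing study outcomes". SAP 6.3 then states that "time-to-event analyses anchored on the index date of isavuconazole initiation will be performed using the KM method". For death, patients are censored when last known alive. Neither document mentions delayed entry.

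**The concern.** SAP 4.2 lets qualification, follow-up and risk begin together. That is true of a patient started at the site. It is not true of a patient started at another hospital who arrives on treatment, because the site holds a chart only if the patient lived long enough to reach it. Kaplan-Meier from initiation would place such a patient in the risk set from day 0, adding person-time in which no death could have been recorded. This is left truncation handled as if it were complete follow-up.

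All-cause mortality is a primary outcome, reported at weeks 6, 12 and 24. The planned confidence intervals do not reflect this error, and it does not shrink as the sample grows. The limitations in Protocol 9.11 cover ward changes, discharge on treatment and undocumented care elsewhere, but not arrivals. Protocol 10.2 does recognise the same kind of selection on survival where consent is needed.

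**Working it through.** **The plan's own precision figures.** The Wilson 95% width is 2z·√(p(1−p)/n + z²/(4n²)) / (1 + z²/n). With p = 0.19 it gives 8.98, 9.96, 12.41 and 14.83 points at n = 292, 237, 152 and 106, against 9.0, 10.0, 12.5 and 15.0 in Protocol Table 1. The table reproduces. The half-width is 6.25 points at n = 150 and 3.2 at about 583, the number of records estimated in Protocol 9.2.1. For mucormycosis (33%, n = 37) it is 14.5 (Wilson) or 15.2 (Wald), against the stated 15%. These are the yardsticks for the bias.

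**Inputs for the bias.** From Protocol 9.5: day-42 mortality P = 19% (aspergillosis) and 33% (mucormycosis). Assumed, because the documents are silent:
- share of included patients transferred in, f = 5% to 30%;
- days from initiation to arrival, d = 3 to 21;
- Weibull survival with shape k = 1.0 (constant hazard) or 0.6 (hazard weighted to the early days);
- the same underlying hazard in transferred and site-initiated patients.

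**Formulas.** S(t) = exp[ln(1−P)·(t/42)^k]. A transferred patient is seen only after surviving to day d, so that patient's apparent day-42 mortality is 1 − S(42)/S(d). The pooled estimate is (1−f)·P + f·[1 − S(42)/S(d)].

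**Worked example.** P = 0.19, d = 14, k = 1: S(42)/S(14) = 0.81^(2/3) = 0.869, so transferred patients show 13.1% instead of 19%. With f = 20% the pooled figure is 0.8 × 19.0 + 0.2 × 13.1 = 17.8%, a bias of −1.2 points.

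**Range.** Downward bias in percentage points, shown as k = 1.0 / k = 0.6:

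| P | f | d = 3 | d = 7 | d = 14 | d = 21 |
|---|---|---|---|---|---|
| 19% | 5% | 0.06 / 0.18 | 0.14 / 0.30 | 0.29 / 0.47 | 0.45 / 0.60 |
| 19% | 10% | 0.12 / 0.36 | 0.29 / 0.60 | 0.59 / 0.93 | 0.90 / 1.21 |
| 19% | 20% | 0.25 / 0.72 | 0.58 / 1.21 | 1.18 / 1.87 | 1.80 / 2.42 |
| 19% | 30% | 0.37 / 1.07 | 0.87 / 1.81 | 1.77 / 2.80 | 2.70 / 3.62 |
| 33% | 5% | 0.10 / 0.29 | 0.23 / 0.49 | 0.48 / 0.77 | 0.74 / 1.01 |
| 33% | 30% | 0.58 / 1.72 | 1.39 / 2.94 | 2.87 / 4.63 | 4.46 / 6.08 |

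With f = 0 the bias is zero.

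**Does the remedy work?** A simulation of about 40,000 included patients (true mortality 19%, constant hazard, f = 20%, d = 14) gave 17.8% from Kaplan-Meier as planned. Delayed entry at arrival gave 19.0%, and so did restriction to site-initiated patients.

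**Could it be repaired later from the planned data?** Treatment setting in Protocol 9.4.2 lists wards, outpatient, other and unknown, with no entry for another hospital beyond the free-text option. Protocol 9.4.6 records hospital stays after index but not first contact with the site. SAP 6.6 plans days from initiation to admission, but that interval alone cannot tell a transfer from a readmission of a patient started at the site.

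**The case against.** The best reply is that site initiation was intended. The population sentence is presented as a consequence of the sites being hospital based, and that inference works only if treatment began at the site. SAP 4.2 reads the same way. The diagnosis must be on record at initiation, the only source is the chart abstracted by local staff, the CRF asks for the ward at the index date, and SAP section 3 lists a subgroup defined by initiation in the ICU. This stands as evidence of intent. It does not bar anyone: records sent with a transferred patient could satisfy every item, and abstractors apply the criteria rather than an unstated premise.

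It is also fair that the bias is small beside the planned precision. Every 19% scenario lies below the 5.00–6.25 point margin in Protocol 9.5, and only the most extreme (3.6 points) exceeds the 3.2-point half-width at about 583 patients. The 33% scenarios lie well inside the 15% precision stated for mucormycosis.

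A reader might infer three stronger things that the documents do not support:
- *That primary mortality is biased down.* No document shows that any transferred patient is in the cohort. Only the survival-to-arrival component has a fixed direction; transferred patients may be sicker or fitter, so the net effect of including them can go either way.
- *That mucormycosis is worse affected because such patients are usually referred.* Neither document says so. The larger figure at 33% follows only from the higher mortality.
- *That a patient treated at two participating hospitals would be counted twice without detection.* Protocol 9.10 says "No patient identifiers used by sites will be entered", but it also has the system assign a study number to each patient, and sites keep the linking list. No transfer between participating sites is described, and undetectability is not shown.

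**Conclusion.** The concern holds in conditional form. The analysis relies on initiation at the site, the criteria do not require it, and no delayed entry is planned. If patients who started elsewhere are included, their time before arrival lowers the all-cause mortality estimate. On the assumed shares, delays and hazard shapes, that component is about 0.1 to 3.6 points at 19% and 0.1 to 6.1 points at 33%, and zero without transfers. The true size cannot be derived from the documents. The case for acting rests on a cheap remedy, a primary outcome, and planned data that would not reliably allow a correction afterwards.

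**What to change.** **Preferred.** Add a CRF item asking whether isavuconazole was initiated at the participating hospital and, if not, how many days passed from initiation to first care there. A duration fits Protocol 9.10, under which dates are not stored. In SAP 6.1 and 6.3, enter these patients into the risk set at that time in all Kaplan-Meier and Cox analyses, including time to first AE in SAP 6.4. Add a sensitivity analysis limited to site-initiated patients. The simple counts at weeks 6, 12 and 24 cannot be corrected by delayed entry, so show them by place of initiation as well.

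Cost: one CRF item and slightly more programming. If the form is already in use, the item can be put to sites as a query, since they hold the link to the chart. Delayed entry removes the event-free interval but not case-mix differences, which is why the sensitivity analysis is needed too.

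**Alternative.** Make the assumption explicit: add to criterion 3 in Protocol 9.2.2 and SAP section 3 that the first dose for the infection was given or prescribed at the participating hospital. Cost: any transferred patients are lost. That loss may not be small for mucormycosis, where Protocol 9.5 intends to include every eligible patient.
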